Due to the nature of the programs, it is not feasible to blind the subjects, implanting physicians or the clinical site personnel to the SGX-SCS programming and Standard programming SCS group assignments. Each SCS group will be programmed under the direction of physicians with support of clinical representatives of the Test and Control treatments, which may identify the type of treatment to study participants. Also, open communication about sensation of paresthesia and pain relief is important in adjusting program parameters to provide optimal pain relief for subjects. The assessments of device performance are done by the subjects and not by the site personnel so the lack of blinding of site personnel should not affect results as pain is the major assessment and subjects tend to describe pain truthfully since it affects their everyday life dramatically and not be influenced by knowledge of the device programming. Despite the inability to blind the study, past SCS studies indicate that there is no reason to believe that subjects and Investigators/clinical staff will be influenced one way or another by the knowledge that a particular SCS program has been used.

B.5.5. Sample Size

Primary Endpoint Assessment occurs at the follow up visit 3 months after Device Activation. Based on the primary endpoint requirement, the estimated sample size of this study is at least 100 total subjects (at least 50 subjects in the SGX-SCS group and at least 50 subjects in Standard SCS group) who have passed screening requirements, have been randomized, and have completed the primary endpoint assessment.

The clinical investigational plan requires a screening process for all subjects that provide written informed consent. These subjects will undergo screening to assess eligibility. Subjects may be excluded for various reasons during screening. Accordingly, in order to include an estimated 125 subjects to the point of randomization and trial phase, approximately 250 subjects may need to be consented and enrolled to account for exclusions prior to randomization.

B.5.5.1 Sample size rationale and statistical power

The sample size estimate to determine primary endpoint is based on the primary objective of demonstrating non-inferiority of the test group to the control group. Established methods were followed in determining the non-inferiority criteria and the related sample size estimate

- Test basis: Farrington-Manning binomial test for non-inferiority

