- Estimated responder rate of 70% in the test group and 50% in the control group
- Significance level, alpha, of 0.05 one-sided
- Statistical power = approximately 90% or greater
- Non-inferiority margin of 10%
- Randomization: 1:1

Based on these assumptions, a minimum of 50 randomized and trialed subjects per treatment group (100 total) are required.

B.5.5.2 Overall Sample Size and Enrollment

Based on the primary endpoint requirement, a minimum of 50 subjects per treatment group are required (100 total). To account for a combined estimated attrition of 20% for subjects that do not complete the Trial Phase, and subjects that exit study before the 3-month primary endpoint visit, a total of 125 subjects would need to be randomized.

To account for 50% attrition prior to randomization (including subject ineligibility after signing the informed consent and subject dropout), it is estimated that a total of up to 250 subjects would need to be enrolled in the study.

[REDACTED]

[figure not shown]
[REDACTED]

[REDACTED]

[REDACTED]

B.6. Enrollment, Assessments, Randomization, and Clinical Procedure

Enrollment of subjects will occur at the clinical sites after Institutional Review Board (IRB) approvals, and when written informed consent from subjects has been obtained. Prior to enrollment, Investigators and clinical site staff will approach subjects, who have been determined to be candidates for SCS therapy and talk about potential participation in the study. Following informed consent, the eligibility of subjects to participate in the study will be assessed according to inclusion and exclusion criteria outlined in this Investigational Plan. Various assessments including pain intensity, evaluation of medical history and records, and the Investigator's clinical judgment will be used in the selection process.

B.6.2. Consent/Enrollment

Written informed consent for participation in the study must be obtained from subjects before initiation of any study-related activities, including those that assess eligibility. Following informed consent, subjects will be assigned a unique subject identification number and will be considered to be enrolled in the study. Eligibility for advancing to the next stage of the study will be evaluated by the site Investigator based on the defined inclusion and exclusion criteria. Subjects will be assessed for pain intensity and disability.

B.6.3. Entry Criteria Evaluation (0-14 days from Enrollment)

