Subjects will be offered an additional visit at 12 months after device activation. The visit will consist of the same assessments as the 3 and 6 month visits. Subjects will visit the study site where they will be assessed for pain, extent of disability, quality of life, Patient Global Impression of Change, and subject satisfaction. Paresthesia generated by the stimulator will be assessed. Programming adjustments may be made, as needed. Subjects will also be assessed for possible adverse events and medication usage. In situations where there is an ongoing study related adverse event, subjects will be followed until resolution of that adverse event or determination that the subject's condition is stable.

Beyond the 12 month visit, there will be no additional scheduled follow-up visits in the study. Following the last scheduled study visit, subjects will be followed by the Investigator at regular intervals, as dictated by standard of care at each site, in order to facilitate pain management, stimulation adjustments, possible revisions and/or replacements of neurostimulation components. Any additional non-study related

monitoring of the subject will be the responsibility of the subject's personal physician, as dictated by reasonable medical care.

B.6.17. Device Explant

At any time during the study, a subject may elect to withdraw from the study and have the SCS device system explanted. Additionally, an Investigator may elect to explant a device due to an adverse event.

The Investigator must follow the appropriate guidelines set forth by the Medtronic for returning the explanted device and/or lead(s) as well as the accessories (charger, patient remote control).

B.6.18. Early Subject Withdrawal

Although efforts will be made by Investigators and study staff to encourage subjects to remain enrolled in the study, subjects may withdraw early from the study for a number of reasons, including but not limited to:

- Failure of SCS Trial Phase
- Subject request
- Investigator request
- Subject lost to follow-up
- Subject's death
- Adverse events (e.g., intolerable adverse event occurrence that forces subject to stop participation in the study)

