If a subject is considering withdrawing from the study due to unsatisfactory effectiveness of the assigned treatment, the Investigator will make attempts to improve therapy during a study visit. When a subject is withdrawn early from the study, a Study Termination eCRF will be completed describing the reason for discontinuation. Study staff will contact subjects to remind them about their scheduled visits and make sufficient efforts to locate a subject that is not responding to a contact call. If a subject has withdrawn consent for the study, or is lost to follow-up, the completion of this visit is not required. In situations where study withdrawal is due to an adverse event, subjects will be followed until resolution of the adverse event or determination that the adverse event is not likely to change.

B.6.20. Study Suspension and Termination

Subjects will be considered to have completed all study requirements following the completion of the follow up visit 6 Months after Device Activation. Each clinical site will be considered to have completed study requirements at the end of the required monitored close out visit. The study will be considered terminated when all of the requirements of this Investigational Plan have been fulfilled, all close out visits have been completed and all Sponsor and Investigator reports have been issued and reported to the IRB.

Stimgenics, the Investigators, or the IRB(s) may suspend or terminate the study early at any time. If the study is suspended or terminated prematurely, all subjects that are still enrolled will be terminated from the study. A Study Completion eCRF will be completed

noting that the study has been terminated. If there is an ongoing adverse event related to the device or treatment, the subject will be followed until resolution of the adverse event or determination that the adverse event is not likely to change.

Subsequent follow-up of the subjects after study completion will be the responsibility of the subject's personal physician.

Stimgenics reserves the right to terminate the study but intends only to exercise this right for reasons related to the protection of subjects or valid scientific or business reasons. Stimgenics will notify Investigators and IRBs in writing in the event of study termination.

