Stimgenics reserves the right to stop the enrollment of subjects at any clinical site at any time after the clinical site initiation. Possible reasons for suspending or terminating a clinical site may include, but are not limited to:

- Non-compliance by Investigator
- Failure to obtain proper written informed consent
- Repeated failure to complete or submit eCRFs in a timely manner
- Failure to report SAEs to the Sponsor within 48 hours of knowledge of the event and to reviewing IRB in accordance with its policies
- Repeated failure to comply with clearance of queries generated during monitoring of the study
- Inactivity

B.7. Study Endpoints

B.7.1. Definition of Analysis Populations

- Intent to Treat (ITT): All randomized subjects.
- Modified Intent to Treat (mITT): All randomized subjects who complete the Trial Phase.

B.7.2. Effectiveness Assessment Definitions

- Primary Effectiveness Assessment: For subjects who have a successful Trial Phase and receive a permanent implant, the Primary Efficacy Assessment occurs at the follow up visit 3 months after Device Activation. For subjects who do not have a successful Trial Phase, the Primary Efficacy Assessment occurs at the end of the Trial Phase.

B.7.3. Primary Endpoint

Pain rating on the 10 cm Visual Analog Scale is considered the primary outcome measure. VAS is the most widely used outcome measure in assessing pain due to its documented reliability and validity, ease in administration, and minimal training requirements for the administrator.

- ***Individual Responder:*** A decrease in back pain VAS by at least 50% at 3 months Post-Permanent Device Activation as compared with Baseline.

Overall Study Success: The percentage of Individual Responders in the test group is shown to be statistically non-inferior to the percentage in the control group.

B.7.4. Secondary Endpoints

The following secondary endpoints will be evaluated:

- Comparison of the percentage of Individual Responders between the test and control groups in a statistical test of superiority
- Comparison of change from Baseline in back pain score (VAS) determined at the 3-month visit after device activation, between test and control in a statistical test of non-inferiority. This is calculated as: Change from Baseline in Back Pain VAS = 3-Month Visit Pain VAS – Baseline Pain VAS. A negative result reflects a decrease in the Pain VAS, while a positive result reflects an increase in Pain VAS.

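### Stopping stimulation is not separated from leaving follow-up, so implanted subjects who stop before Month 3 may have an imputed primary result where an observed one could be had

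*Combined protocol and SAP*

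**What the plan says.** Several places bear on what happens when an implanted subject stops therapy.

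- **B.6.17, subject's choice.** "At any time during the study, a subject may elect to withdraw from the study and have the SCS device system explanted". Explant and withdrawal appear as one act.
- **B.6.17, investigator's choice.** The next sentence lets the investigator explant because of an adverse event. It does not say whether the subject then stays in the study.
- **B.6.18.** Adverse events are a listed reason for early withdrawal, with the example "intolerable adverse event occurrence that forces subject to stop participation in the study". On what is recorded: "When a subject is withdrawn early from the study, a Study Termination eCRF will be completed describing the reason for discontinuation". Subjects who withdraw because of an adverse event are followed until it resolves or is unlikely to change.
- **B.6.18, exit visit.** "If a subject has withdrawn consent for the study, or is lost to follow-up, the completion of this visit is not required". This implies a visit for other withdrawals, but the readable text gives neither its timing nor its content.
- **C.1, Pregnancy Risks.** A subject who becomes pregnant switches the device off and is exited.
- **B.7.1.** "Intent to Treat (ITT): All randomized subjects". The synopsis likewise defines the primary endpoint over randomized subjects and counts those without a successful Trial Phase as failures.
- **B.7.2.** For implanted subjects the primary assessment is the visit 3 months after Device Activation.
- **B.9.2.4.** Trial Phase results are used for unsuccessful trials. Other missing data are multiply imputed, and sensitivity analyses are promised. The text that follows is redacted.

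**The concern.** A subject who has been explanted, or has switched stimulation off, still has back pain that can be scored on the Month 3 date. If that subject is treated as having left the study, a score that could have been observed has to be imputed. The missingness is informative, because the reason for stopping is likely to be related to the outcome.

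Adverse-event follow-up does not fill the gap. No pain score is named as part of it, and B.8.3.1 does not require back and leg pain to be reported as adverse events unless serious. A site could therefore remain in contact with such a subject past Month 3 without taking a VAS.

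Two kinds of treatment failure would also be handled differently. A failed Trial Phase counts as a non-response. A failure after implant, if it leads to exit, receives an imputed value. If the imputation draws mainly on subjects still receiving stimulation, it will tend to credit stoppers with responses that they did not have. In a non-inferiority test this favours whichever arm has more stoppers. The Month 3 change in VAS, the Month 3 ODI and the Month 6 endpoints lose the same subjects.

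**Working it through.** **1. The plan's own figures.** B.5.5.1 gives: "Test basis: Farrington-Manning binomial test for non-inferiority"; "Estimated responder rate of 70% in the test group and 50% in the control group"; one-sided alpha 0.05; margin 10 points; 1:1 allocation; about 90% power or greater; 50 per group. With the restricted maximum-likelihood null variance, power at 50 per group is 92.7%, which agrees with the plan. Inflating for 20% attrition gives 100 / (1 − 0.20) = 125, also as stated, or about 62 per arm (125 / 2 = 62.5). The sample size is not in question here.

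**2. What is not given.** The 20% in B.5.5.2 combines subjects who do not complete the Trial Phase with those who exit before Month 3. The share who stop after implant is not stated, so every stopping rate below is an assumption.

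**3. Illustration at the edge of the margin.** Assumptions:
- true rates over all randomized subjects of 40% (SGX) and 50% (control), a difference of −10 points;
- 4 of 62 SGX and 1 of 62 control subjects stop before Month 3;
- stoppers are non-responders;
- stoppers are imputed at the completer rate.

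Completer rate = true rate / (1 − proportion stopping):
- SGX: 0.40 × 62 / 58 = 42.8%
- Control: 0.50 × 62 / 61 = 50.8%
- Apparent difference: 42.8 − 50.8 ≈ −8.1 points before rounding, a shift of about 1.9 points toward non-inferiority.

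The probability of declaring non-inferiority is the sum, over all pairs of responder counts, of the two binomial probabilities wherever the Farrington-Manning statistic exceeds its one-sided 5% critical value:

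| Per arm | No stopping (40% v 50%) | With the shift (42.8% v 50.8%) |
|---|---|---|
| 50 | 4.7% | 6.8% |
| 62 | 5.8% | 8.8% |

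The increases are 2.1 and 3.0 points. At 62 per arm the test is already slightly above 5% without stopping, so only the increase belongs to this point. The table treats imputed values as observed. Proper multiple imputation adds variance and would tend to lower the right-hand column somewhat.

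**4. Other patterns.** Same logic, 50 randomized per arm, control completer rate 50%, true difference −10 points with stoppers as non-responders, imputation approximated by testing completers only:

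| Stop, SGX / control | False non-inferiority |
|---|---|
| 0% / 0% | 4.7% |
| 5% / 5% | 4.1% |
| 10% / 10% | 3.7% |
| 0% / 10% | 1.6% |
| 5% / 0% | 7.0% |
| 10% / 5% | 8.0% |
| 10% / 0% | 12.3% |

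At this boundary, balanced stopping or more stopping in control is conservative. The error rate rises only when SGX subjects stop more often.

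**5. At the design rates (70% v 50%).** The estimated difference shifts toward SGX by 0.70 × SGX stopping − 0.50 × control stopping: 1.0 point at 5% in each arm, 2.0 points at 10% in each, and 4.5 points at 10% v 5%. This affects the estimate. It is not a false-positive rate, because SGX is truly better at those rates.

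**The case against.** The strongest reply is that the plan contains no rule exiting everyone who stops therapy. B.6.17 gives the subject an option and describes someone who has chosen to leave. Its sentence on investigator explant exits nobody. B.6.13 does not make the Month 3 visit depend on a working device, B.6.18 commits staff to encouraging subjects to stay, and B.9.2.4 promises rigorous follow-up. This is right as far as it goes, and what remains is an ambiguity: the text does not say that follow-up continues, and sites may read it differently.

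Stronger readings that the documents do not support:

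- **That no outcome is collected from any stopper.** B.6.18 implies an exit visit. Sections B.6.16 and B.6.19 and the data-collection table are not in the readable text. The finding is that no readable passage requires a Month 3 or Month 6 score after stopping.
- **That the primary result becomes a guess.** Multiple imputation and sensitivity analyses are planned, and redaction of their detail is not a fault. That the imputation would lean on subjects still on therapy is an inference.
- **That 25 of 125 subjects are at risk.** The 20% allowance also covers Trial Phase non-completers.
- **That the shift is 3.7 points.** That figure (4/62 × 0.70 − 1/62 × 0.50) uses the design rates. Carrying a shift of about 3 points to the 40% v 50% boundary gives 8.3% (50 per arm) or 10.9% (62 per arm), but it mixes two scenarios. Applied consistently, the shift is 1.9 points.
- **That B.6.20 shows the same fault.** It concerns suspension or termination of the whole study and says nothing about an individual who stops therapy.

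It is also fair that both arms use the same implanted system, so hardware causes such as pocket infection give no stated reason for imbalance. This limits how likely the adverse scenario is, but in an open-label comparison of programming approaches imbalance cannot be excluded in advance.

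**Conclusion.** The concern holds as a gap in data collection. B.6.17 and B.6.18 do not distinguish stopping stimulation from leaving follow-up, and no readable passage secures a Month 3 or Month 6 outcome from implanted subjects who stop. Where these subjects exit, their primary result is multiply imputed, whereas Trial Phase failures count as non-responders.

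The size is conditional. It rests on assumed stopping rates, on stoppers being non-responders and on imputation near the completer rate; none of these comes from the documents. Under the 4/62 v 1/62 illustration the inflation is modest. It would be larger with stronger imbalance toward SGX, and absent at the boundary with balanced stopping. The sample size calculation is unaffected. The change should be made because the direction cannot be known beforehand and sensitivity analyses cannot replace a score that was obtainable.

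**What to change.** - In B.6.17 and B.6.18, state that explant (by subject or investigator), switching stimulation off, or an adverse event ends study therapy but not study follow-up. Align the pregnancy paragraph in C.1 on follow-up only.
- Unless consent is withdrawn, collect back and leg VAS, ODI, medication use and adverse events on the Month 3 and Month 6 dates counted from Device Activation, by telephone or mail if needed.
- Define the exit visit that B.6.18 mentions, and record back VAS at it for subjects who do leave.

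No change to B.6.20 is needed for this point. The request concerns data collection only, not when to explant or stop stimulation.

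The cost is protocol wording and a few off-therapy contacts, since the visits are already scheduled. The responder rate may come out slightly less favourable.

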The implantation of a spinal cord stimulation system involves risks that are similar to other spinal procedures. In addition to those normally associated with surgery, implantation or use of a neurostimulation system includes, but is not limited to, the following risks:

- Allergic or immune system response to the implanted materials
- Infection
- Lead or neurostimulator erosion through the skin or migration
- Leakage of cerebrospinal fluid
- Loss of pain relief may return patients to their underlying pain condition
- Persistent pain at the neurostimulator site
- Placement of the epidural lead is a surgical procedure that may expose patients to risks of epidural hemorrhage (bleeding), hematoma, or paralysis
- Radicular chest wall stimulation
- Seroma (fluid collection in pocket where stimulator is placed) or hematoma at the neurostimulator site
- Change in stimulation, possibly related to cellular changes around the electrode(s), shifts in electrode position, loose electrical connections, lead fractures, which has been described by some patients as uncomfortable stimulation (jolting or shocking sensation)
- Over time there could be changes in the level of symptom control. In most cases, the physician can correct these changes without surgery.
- Formation of excessive tissue around the lead in the epidural space can result in delayed spinal cord compression and paralysis, requiring surgical intervention. Time to onset can range from weeks to many years after implant.
- The safety of this therapy is unknown for pregnancy, unborn fetus, or delivery
- Stimulation-dependent gastrointestinal symptoms such as diarrhea, incontinence or constipation
- Stimulation-dependent bladder symptoms such as urinary retention, incontinence or frequency
- Unexpected changes in stimulation - Electromagnetic interference, changes in posture, and other activities can cause a perceived increase in stimulation

System Revision Risk

The Intellis AdaptiveStim Neurostimulator may require replacement in 9 years or earlier, regardless of the number of times the neurostimulator is recharged. It is possible that the system will need to be revised (explanted, replaced, or repositioned) earlier than 9 years. Possible reasons for revision/explant may include infection, malfunction, and migration of the system components. The risks associated with system revision are equivalent to the commercially available systems.

Pregnancy Risks

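### B.6.20 gives a suspension the same consequence as termination, so a study-wide hold would stop scheduled visits and new adverse-event capture in implanted subjects and forfeit 3-month assessments not yet made

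*Combined protocol and SAP*

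**What the plan says.** B.6.20 (Study Suspension and Termination) grants a broad power: "Stimgenics, the Investigators, or the IRB(s) may suspend or terminate the study early at any time". The sentence that follows gives both events the same result: "If the study is suspended or terminated prematurely, all subjects that are still enrolled will be terminated from the study". A Study Completion eCRF is then filed "noting that the study has been terminated"; no status for a suspended study is mentioned.

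There is one exception. "If there is an ongoing adverse event related to the device or treatment, the subject will be followed until resolution of the adverse event", or until the event is judged unlikely to change. Beyond that, "Subsequent follow-up of the subjects after study completion will be the responsibility of the subject's personal physician".

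Other sections fix what such a rule would interrupt:

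- **B.7.2:** for subjects with a successful Trial Phase and an implant, "the Primary Efficacy Assessment occurs at the follow up visit 3 months after Device Activation". Subjects whose Trial Phase fails are assessed at its end.
- **B.6.14, B.6.15 and B.7.4:** a 6-month visit supplies secondary endpoints, and an additional 12-month visit is offered.
- **B.8.3.2:** adverse events are captured from enrollment until the study is completed.
- **B.7.1 and B.9.2.4:** ITT is all randomized subjects. Missing data other than Trial Phase failures are multiply imputed, with sensitivity analyses.

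**The concern.** Suspension and termination serve different purposes. A suspension holds the study while a question is answered and may be lifted; a termination ends it. Under B.6.20 the effect on subjects is the same and cannot be undone, because once all enrolled subjects have been exited nobody is left under observation when the hold is lifted.

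Two things are at stake.

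**Safety data.** Implanted subjects would still have the system in place, but a new adverse event after the suspension would have no study route for capture. Section C.1 lists delayed spinal cord compression among the risks and says of it: "Time to onset can range from weeks to many years after implant". It also names periodic monitoring of participants among its risk controls. The plan has no Data Monitoring Committee (stated just before B.9), so suspension is a main way of responding to a signal, and the present rule would switch that monitoring off at the same moment.

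**Endpoint data.** Every implanted subject who has not reached the 3-month visit would lose the observed primary outcome, and outstanding 6- and 12-month assessments would go as well.

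**Working it through.** **1. The plan's own sample size.** B.5.5.1 gives responder rates of 0.70 (test) and 0.50 (control), a margin of 0.10, one-sided alpha of 0.05 and 50 per group. For the Farrington-Manning test, the restricted estimates under a difference of -0.10 are 0.644 (control) and 0.544 (test).

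- Null standard error: sqrt[(0.644 x 0.356 + 0.544 x 0.456)/50] = sqrt(0.4773/50) = 0.0977
- Standard error under the alternative: sqrt[(0.70 x 0.30 + 0.50 x 0.50)/50] = sqrt(0.46/50) = 0.0959
- Power = Phi[(0.20 + 0.10 - 1.645 x 0.0977)/0.0959] = Phi(1.452) = 92.7%

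This agrees with the stated power of about 90% or more. The same formula gives 90.2% at 45 per group. The inflation also reproduces: 100/(1 - 0.20) = 125, matching "a total of 125 subjects would need to be randomized" in B.5.5.2, and 125/(1 - 0.50) = 250.

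**2. Time from randomization to the 3-month assessment.** The windows come from B.6.6 (Trial Phase up to 10 days), B.6.8 (implant 0-60 days later), B.6.9 (activation 0-14 days later) and B.6.13 (3 months plus or minus 15 days). I take 3 months as 90 days and assume that the Trial Phase starts at randomization, since the visible text gives no window for that step.

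- Longest path: 10 + 60 + 14 + (90 + 15) = 189 days
- Short path with a 10-day trial: 10 + 0 + 0 + (90 - 15) = 85 days

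**3. Subjects caught by a mid-accrual suspension.** The documents give no accrual period. As an assumption, take 125 subjects accrued evenly over 12 months (365 days) or 18 months (548 days). The number randomized by mid-accrual is 125 x 0.5 = 62.5, which caps every count. Otherwise the count is 125 x path/accrual period.

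| Assumed accrual | 85-day path | 189-day path |
|---|---|---|
| 12 months | 125 x 85/365 = 29.1 | all 62.5 (189 days exceeds the 182.5 elapsed) |
| 18 months | 125 x 85/548 = 19.4 | 125 x 189/548 = 43.1 |

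The range is roughly 19 to at most about 62. The upper end puts every subject at the limit of every window. No Trial Phase failures or dropouts have been deducted.

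**4. What lost assessments would cost (illustration only).** Assume that the losses fall equally on the two groups, that imputation recovers nothing and that lost subjects are not replaced.

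| 3-month assessments lost out of 100 | Per group | Power |
|---|---|---|
| 0 | 50 | 92.7% |
| 10 | 45 | 90.2% |
| 20 | 40 | 86.9% |
| 30 | 35 | 82.7% |
| 40 | 30 | 77.3% |
| 50 | 25 | 70.4% |

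These losses are counted against the 100 completers, whereas step 3 counts randomized subjects before deductions, so the two tables should not be matched row for row.

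**The case against.** The strongest reply is that this is contingent drafting. It bites only if a study-wide suspension occurs, is applied literally and is later lifted; no hypothesis, analysis or sample size changes. That is fair, and it limits the weight of the point. It does not remove it, because B.6.20 states a rule rather than leaving a gap, and staff following it would exit subjects.

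Several stronger readings are tempting but are not supported:

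- **That endpoint data would be destroyed.** Nothing discards collected data. Terminated subjects remain in ITT, Trial Phase failures already have their primary assessment, and missing values are imputed with sensitivity analyses. Only assessments not yet made are at risk.
- **That all follow-up of implanted subjects would end.** Ongoing adverse events related to the device or treatment are still followed, and B.8.3.2 allows sites to report device-related events to the manufacturer.
- **That the sponsor cannot pause at all.** B.6.20 also lets the sponsor stop enrollment at any site. This is a partial pause, but it does not cover a study-wide suspension by an IRB or the investigators.
- **That B.6.20 contradicts C.1.** The long-latency risk in C.1 would outlast even an uninterrupted study, and its monitoring measure concerns people in the study. The rule undercuts C.1; it does not conflict with it.
- **That the sample size has no slack.** 125 x 0.80 = 100 exactly meets the completer target, but about 45 per group already gives 90% power.

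One caution also stands. Section numbering skips from B.6.18 to B.6.20, and the withdrawal text refers to a visit not described in what can be seen. Exit-visit wording may exist elsewhere, in which case part of the fix would only need a cross-reference.

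**Conclusion.** The point holds as a defect in the study-status rule. B.6.20 attaches one irreversible consequence to two different events and, in the visible text, provides neither for continued data collection during a hold nor for resumption. Applied as written, a study-wide suspension would stop scheduled visits and capture of new adverse events in implanted subjects, and primary assessments still outstanding would be imputed rather than observed.

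The size cannot be fixed from the documents. The figure of roughly 19 to at most about 62 subjects rests on assumed even accrual over 12 to 18 months, a suspension at mid-accrual and the plan's visit windows. On the illustrative power figures, losing 10 of 100 completers still leaves about 90%; larger losses fall below it. The planned sample size itself is sound and is not in question. The change is worth making because it is cheap and because a suspension is a poor time to improvise such a rule.

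**What to change.** Split the rule in B.6.20.

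- **Suspension:** stop new consent and randomization. Keep subjects already randomized enrolled, including those awaiting a trial or implant, with scheduled visits, VAS collection and adverse-event capture continuing unless the IRB directs otherwise. Record the suspension as its own status and state how the study resumes. Leave treatment decisions during a hold to the sponsor, investigators and IRB.
- **Termination:** keep the present rule, but obtain a final adverse-event and VAS assessment for each implanted subject, where feasible, before the Study Completion eCRF is filed. If exit-visit text already exists, refer to it.

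The cost is about one paragraph of protocol wording and an eCRF status. The small downside is that visits already planned continue during a hold. The sample size and the primary analysis do not change.
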